8.2 SAFETY AND OTHER ASSESSMENTS

The baseline value of each assessment will be the value assessed closest and prior to the first dose of TWB-103.

8.2.1 INFORM CONSENT

The investigator must explain to each subject the nature of the study, its purpose, the procedures involved, the expected duration, the potential risks involved, and any predicted discomforts. Each subject will be informed that participation in the study is voluntary and that he/she can withdraw their participation at any time.

All subjects must provide signed and dated informed consent prior to any study-related procedures. Only the Independent Ethics Committee (IEC) or Institutional Review Board (IRB) and the applicable regulatory authorities approved ICF can be used.

8.2.2 SCREENING, ELIGIBILITY, AND ENROLLMENT

Screening is defined as the process for identifying a candidate for the study and evaluating their eligibility to participate. Eligibility should be thoroughly checked by the investigators during screening and at Day 1 Visit before the application of TWB-103 based on the inclusion and exclusion criteria. Procedures for screening can be done between signing ICF and Day 1. However, procedures should be completed before

the TWB-103 application if performed on Day 1; in this case, the same procedures scheduled for Day 1 can be waived. The eligibility re-check at Day 1 Visit will be based on the results from Day 1 Visit (vital signs and physical exam) and other information collected during screening. A subject is recognized as enrolled into the study if this subject consented and is screened, with eligibility verified.

8.2.3 DEMOGRAPHICS

Demographic data, including the subject's birth year, race, and gender, will be recorded at the Screening Visit.

8.2.4 MEDICAL HISTORY

General medical history within 1 year before Screening Visit and malignancy on a life time basis should be recorded at Screening Visit. The history of diabetic lower limb ulcer for the lifetime base will be recorded in the "diabetic lower limb ulcer" part of the CRF, separately. All history recorded will include date of onset, diagnosis and current status.

8.2.5 LABORATORY, PREGNANCY AND PANEL REACTIVE ANTIBODY TESTS

Laboratory tests to be measured in this study will consist of the followings:

- Hematology: hemoglobin, hematocrit, RBC, platelet, and WBC with differential counts, ANC
- Biochemistry: total bilirubin, ALT, AST, fasting glucose, HbA1c, serum albumin, blood urea nitrogen (BUN), and serum creatinine

Laboratory and pregnancy tests performed within 1 week prior to Week 5 Visit, or within 1 week prior to Week 12 or End-of-Treatment visit, are acceptable.

Pregnancy tests can be done with serum or urine. Pregnancy tests can be waived if the female subject has menopausal for over 1 year, total hysterectomy, bilateral salpingo-oophorectomy or other clinical condition that completely eliminates childbearing potential, confirmed by the investigator.

For panel reactive antibody (PRA) test, all patients will be tested with class I human leukocyte antigen (HLA). PRA test performed within 1 week prior to Week 12 or End-of-Treatment visit, are acceptable.

When withdrawal occurs during TWB-103 treatment period, laboratory, pregnancy and PRA tests done within 1 week prior to EOS visit are acceptable.

8.2.6 PHYSICAL EXAMINATION, HEIGHT, AND WEIGHT

Height and weight will be collected at Screening Visit only.

Physical examination conducted in this study will include general appearance, skin, eyes, ears, nose, throat, head and neck, heart, chest and lungs, abdomen, extremities, lymph nodes, musculoskeletal, neurological, etc.

8.2.7 VITAL SIGNS

Vital signs measurement will consist of systolic/diastolic blood pressure, respiratory rate, pulse rate or heart rate, and body temperature. Respiratory rate, pulse/heart rate and blood pressure (systolic/diastolic) will be obtained after the subject has been at rest for at least 5 minutes in a sitting position.

8.2.8 ANKLE BRACHIAL INDEX

The ankle-brachial index (ABI) is the ratio of the blood pressure at the ankle to the blood pressure in the upper arm. The ABI is calculated by dividing the systolic blood pressure at the ankle by the systolic blood pressure in the arm.

8.2.9 STANDARD OF CARE

The choice of standard-of-care will be at investigator's discretion based on the physical condition of the subject. Subjects will receive standard of care for at least two weeks during screening as part of the eligibility check. If required, the investigator can provide standard of care to the subject during the TWB-103 treatment period. However, revascularization is prohibited during treatment period (Visit 2~Visit 13). The investigator will also provide standard of care to subjects in the follow-up period as a protection for subjects who have confirmed wound healing or as a treatment for those still have open wound. Refer to section 6.7 for details of standard of care.

8.2.10 ASSESSMENT OF ADVERSE EVENT

All AEs will be assessed for severity by the study investigator based on National Cancer Institute Common Terminology Criteria for Adverse Events (NCI-CTCAE) 5.0. Further, the investigator has to judge if the AE is IP (TWB-103)-related. Refer to section 8.4 for details of AE definition and reporting.

8.3 STUDY SCHEDULE

The assessments or procedures to be performed at each study visit are listed below. The results of protocol specific assessments and procedures will be recorded in the source documents for all study

subjects and on the appropriate page of the CRF. Unscheduled visit will be arranged when investigator considered necessary.

8.3.1 SCREENING VISIT (VISIT 1)

The Screening Visit will be scheduled after signing ICF and within 4 weeks prior to Day 1 (Day -28 ~ Day 1). Procedures performed between signing ICF and Day 1 are acceptable. However, procedures should be completed before the TWB-103 application if performed on Day 1; in this case, the same procedures scheduled for Day 1 can be waived.

- Obtain signed informed consent
- Assign identifier number
- Demographics
- Medical history
- Medication history
- Physical examination
- Vital signs
- Pregnancy test (for applicable subjects only)
- Laboratory test
- PRA test
- Eligibility
- Ulcer evaluation (wound size, wound volume (optional), granulation rate and quality of granulation tissue, and grading; before and after standard of care for at least 2 weeks)
- Ankle Brachial Index
- Standard of care for at least 2 weeks
- Concomitant medication
- Adverse event

8.3.2 TREATMENT DAY 1 VISIT (VISIT 2)

- Physical examination
- Vital signs
- Standard of care (when standard of care is required, revascularization is prohibited during treatment period)
- Ulcer evaluation (wound size, wound volume (optional), granulation rate and quality of granulation tissue)
- Eligibility
- TWB-103 application

- Concomitant medication
- Adverse event

8.3.3 TREATMENT VISITS (VISIT 3~13)

Additional treatment visits will be performed weekly from week 1 ~ week 11.

(Day 8, 15, 22, 29, 36, 43, 50, 57, 64, 71, 78, all with a visiting window of \pm 2 days)

- Physical examination
- Vital signs
- Pregnancy test (for applicable subjects only; only for Week 5, performed within 1 week before scheduled visit is acceptable)
- Laboratory tests (only for Week 5, performed within 1 week before scheduled visit is acceptable)
- Standard of care (when standard of care is required, revascularization is prohibited during treatment period)
- Ulcer evaluation (wound size, wound volume (optional), granulation rate and quality of granulation tissue)
- TWB-103 application
- Concomitant medication
- Adverse event

8.3.4 WEEK 12/END OF TREATMENT VISIT (VISIT 14)

(Day 85, with a visiting window of \pm 2 days, or for early confirmed wound closure)

(If the withdrawal is decided during TWB-103 treatment period, the withdrawn subject will be encouraged to complete the assessments of Week 12, within 1 week of the withdrawal decision, as End of Study visit, before exiting from the study.)

- Physical examination
- Vital signs
- Pregnancy test (for applicable subjects only; performed within 1 week before scheduled visit is acceptable)
- Laboratory tests (performed within 1 week before scheduled visit is acceptable)
- PRA test (performed within 1 week before scheduled visit is acceptable)
- Standard of care (if necessary)
- Ulcer evaluation (wound size, wound volume (optional), granulation rate and quality of granulation tissue)
- Concomitant medication
- Adverse event

8.3.5 FOLLOW-UP VISITS (VISIT 15-21)

(Week 13, 14, 16, 20, 24, 30, 36 or 1 week, 2 weeks, 4 weeks, 8 weeks, 12 weeks, 18 weeks, 24 weeks after End-of-Treatment for early confirmed wound closure)

(Day 92 (\pm 2), 99 (\pm 2), 113 (\pm 3), 141 (\pm 6), 169 (\pm 6) 211 (\pm 6), 253 (\pm 6) or 7 (\pm 2), 14 (\pm 2), 28 (\pm 3), 56 (\pm 6), 84 (\pm 6), 126 (\pm 6), 168 (\pm 6) after End-of-Treatment for early confirmed wound closure)

(If the withdrawal is decided during the follow-up period, the withdrawn subject will be encouraged to complete the assessments of Week 36, within 2 weeks of the withdrawal decision, as End of Study visit, before exiting from the study.)

- Physical examination
- Vital signs
- Standard of care (if necessary)
- Ulcer evaluation (wound size, wound volume (optional), granulation rate and quality of granulation tissue)
- Concomitant medication
- Adverse event

8.3.6 UNSCHEDULED VISIT

Unscheduled visits will be arranged when investigators consider necessary.

- Physical examination
- Vital signs
- Concomitant medication
- AE/SAE reporting
- Other actions to be performed will be per investigator's decision

8.4 ADVERSE EVENTS AND SERIOUS ADVERSE EVENTS

8.4.1 DEFINITION OF ADVERSE EVENTS (AE)

Based on ICH GCP, adverse event (AE) means any untoward medical occurrence in a patient or clinical investigation subject administered a pharmaceutical product or intervention and which does not necessarily have a causal relationship with this treatment. An adverse event (AE) can therefore be any unfavorable and unintended sign (including an abnormal laboratory finding), symptom, or disease temporally associated with the use of a medicinal (investigational) product/intervention, whether or not related to the medicinal (investigational) product/intervention.

Pre-existing abnormalities are considered as AE only when the conditions escalate.

Increment in wound size by 30% comparing to baseline should be reported as an AE irrespective of causality to the investigational products.

8.4.2 DEFINITION OF SERIOUS ADVERSE EVENTS (SAE)

An adverse event (AE) or suspected adverse reaction is considered "serious" if, in the view of either the investigator or sponsor, it results in any of the following outcomes (based on ICH GCP):

- Death
- Is life-threatening
- Requires inpatient hospitalization or prolongation of existing hospitalization
- Results in persistent or significant disability/incapacity
- Is a congenital anomaly/birth defect
- Based upon appropriate medical judgment, the event may jeopardize the subject and may require medical or surgical intervention to prevent one of the outcomes listed above

8.4.3 CLASSIFICATION OF AN ADVERSE EVENT

8.4.3.1 Severity of Event

All AEs will be assessed for severity by the study investigator using the following guidelines (based on NCI-CTCAE 5.0):

- **Grade 1 (Mild)**: Asymptomatic or mild symptoms; clinical or diagnostic observations only; intervention not indicated
- **Grade 2 (Moderate)**: Minimal, local or noninvasive intervention indicated; limiting age-appropriate instrumental ADL*
- **Grade 3 (Severe)**: Hospitalization or prolongation of hospitalization indicated; disabling; limiting self-care ADL**
- **Grade 4 (Life threatening)**: Urgent intervention indicated
- **Grade 5 (Death)**: Death

*Instrumental ADL refer to preparing meals, shopping for groceries or clothes, using the telephone, managing money, etc.

**Self-care ADL refer to bathing, dressing and undressing, feeding self, using the toilet, taking medications, and not bedridden.

8.4.3.2 Relationship to Study Intervention

All adverse events (AEs) must have their relationship to study product assessed by the investigator who examines and evaluates the subject based on temporal relationship and his/her clinical judgment. The degree of certainty about causality will be graded using the categories below. In a clinical trial, the study product must always be suspect.

- **Definitely Related**: There is clear evidence to suggest a causal relationship, and other possible contributing factors can be ruled out. The clinical event, including an abnormal laboratory test result, occurs in a plausible time relationship to study agent/intervention administration and cannot be explained by concurrent disease or other drugs or chemicals. The response to withdrawal of the study agent/intervention (dechallenge) should be clinically plausible. The event must be pharmacologically or phenomenologically definitive, with use of a satisfactory rechallenge procedure if necessary.
- **Probably Related**: There is evidence to suggest a causal relationship, and the influence of other factors is unlikely. The clinical event, including an abnormal laboratory test result, occurs within a reasonable time sequence to administration of the study agent/intervention, is unlikely to be attributed to concurrent disease or other drugs or chemicals, and follows a clinically reasonable response on withdrawal (dechallenge). Rechallenge information is not required to fulfill this definition.
- **Possibly/Potentially Related**: There is some evidence to suggest a causal relationship (e.g., the event occurred within a reasonable time after administration of the trial medication). However, the influence of other factors may have contributed to the event (e.g., the subject's clinical condition, other concomitant events). Although an adverse drug event may rate only as "possibly related" soon after discovery, it can be flagged as requiring more information and later be upgraded to "probably related" or "definitely related", as appropriate.
- **Unlikely to be related**: A clinical event, including an abnormal laboratory test result, whose temporal relationship to study intervention administration makes a causal relationship improbable (e.g., the event did not occur within a reasonable time after administration of the investigational product) and in which other drugs or chemicals or underlying disease provides plausible explanations (e.g., the subject's clinical condition, other concomitant treatments).
- **Not related**: The AE is completely independent of study agent/intervention administration, and/or evidence exists that the event is definitely related to another etiology. There must be an alternative, definitive etiology documented by the investigator.

8.4.3.3 Expectedness

Sponsor and investigators will be responsible for determining whether an AE is expected or unexpected. An AE is considered "unexpected" if it is not listed in the investigator's brochure (IB), package insert, or is not listed at the specificity or severity that has been observed; or, if an IB is not required or available, is not consistent with the risk information described in the protocol, as amended.

Expected adverse reactions are AEs that are known to occur for the study intervention being studied and should be collected in a standard, systematic format using a grading scale based on functional assessment or magnitude of reaction. IB will be the source of the reference safety information used to determine the expectedness of the AE. Expectedness is assessed based on the awareness of AEs previously observed, not on the basis of what might be anticipated from the properties of the study intervention.

8.4.4 ADVERSE EVENT REPORTING

AEs may be volunteered spontaneously by the study subject, discovered as a result of general questioning by the study staff, or determined by physical examination. All AEs will be recorded on the CRF. For all AEs, the investigator must pursue and obtain adequate information both to determine the outcome of the AE and to assess whether it meets the criteria for classification as a serious AE requiring immediate notification. Follow-up of the AE, even after the date of study drug discontinuation, is required if the AE persists.

8.4.5 SERIOUS ADVERSE EVENT REPORTING

The investigator will report to the sponsor/CRO contact any SAE within 24 hours of the investigator's knowledge of the event, regardless of the expectedness and causality to the study intervention. The reporting of the SAE to the regulatory authorities/IEC/IRB will comply with the local regulations and requirements.

Nevertheless, the following events will not be reported as a SAE:

- Hospitalization due to social reasons in absence of an adverse event
- Hospitalization due to surgery or procedure planned before entry into the study (must be documented in the CRF)

All SAEs will be followed until satisfactory resolution or until the site investigator deems the event to be chronic or the subject is stable. Other supporting documentation of the event may be requested by sponsor and should be provided as soon as possible.

The sponsor/CRO will be responsible for notifying the regulatory authorities of any unexpected fatal or life-threatening suspected adverse reaction as soon as possible, but in no case later than 7 calendar days after first acknowledged by the Sponsor. A complete report should be provided within 15 calendars by

sponsor's acknowledgement and must include an assessment of the importance and implication of the findings and/or previous experience on the same or similar medical products.

Serious, unexpected suspected adverse reactions that are not fatal or life-threatening must be filed as soon as possible but no later than 15 calendar days after first knowledge by the sponsor that a case qualifies.

8.4.6 PREGNANCY REPORTING

Any patient or patient's partner who becomes pregnant during the treatment period should be recorded and the information regarding this pregnancy should be collected. Any pregnancy occurs during the 30 days following the last dose of investigational product should also be reported and accompanied information should also be collected. When female patient or male patient's partner suspects a pregnancy during the treatment period or within 30 days of the last dose, a pregnancy test should be conducted. Once pregnancy is confirmed, the patient should stop the administration of investigation product immediately, if patient is still during the treatment period. The pregnancy should be reported to the sponsor using the pregnancy report form. The Obstetrician/Gynecologist of the female patient or male patient's partner should be notified the trial information. Because information of specific tests regarding this investigational product is not clear yet, whenever possible, a pregnancy should be followed to term or to any premature terminations reported. Additionally, the status of the mother and child should be reported to the sponsor after delivery. Although pregnancy occurring during the trial is not considered as an adverse event, any pregnancy complications should be recorded as AEs or SAEs.

9 STATISTICAL CONSIDERATIONS

9.1 STATISTICAL HYPOTHESES

Not applicable for this study.

9.2 SAMPLE SIZE DETERMINATION

It is planned to enroll 10 subjects to achieve 8 evaluable subjects.

A subject is considered evaluable if the subject fulfills the criteria of per-protocol population.

9.3 POPULATIONS FOR ANALYSES

The following populations will be introduced for statistical analysis.

Intend-to-treat (ITT) population:

- All enrolled subjects who have received at least one application of TWB-103
- With any post-treatment evaluation

Per-protocol (PP) population:

- A subset of ITT population
- Fulfill all inclusion and exclusion criteria
- Dosed with at least 9 applications of TWB-103, OR with early confirmed wound closure and at least 75% treatment application
- With efficacy endpoint measurement at wound assessment
- Not received any prohibited treatment during TWB-103 treatment period

Safety evaluations will be performed on ITT population. Analysis of efficacy endpoints will be performed on ITT and PP population. The main conclusion will be made on ITT population analysis results of the primary endpoint.

9.4 STATISTICAL ANALYSES

9.4.1 GENERAL APPROACH

There will be a separate formal statistical analysis plan (SAP) to be completed prior to database/data lock. The SAP generally includes additional statistical analysis detail (e.g., more detail of analysis populations, summary of statistical strategies). Any deviations from the planned analysis as described in the SAP will be justified and recorded in the final clinical study report.

The baseline value of each assessment will be the value assessed closest and prior to 1st application of TWB-103.

Descriptive statistics will be provided for all endpoints.

Continuous variables will be summarized by reporting the number of observations, mean, standard deviation, median, interquartile range (IQR = third quartile (Q3) - first quartile (Q1)), Q1, Q3, minimum and maximum.

Categorical variables will be summarized using frequency tables showing the number and percentage of subjects within a particular category.

Ordinal endpoints will be presented by transition tables.

Healing time from baseline to wound closure will be estimated by using Kaplan-Meier method.

The data changes from baseline value will be analyzed by one-sample t-test or Wilcoxon sign rank test. The baseline value of each assessment will be the value assessed closest and prior to 1st application of TWB-103. The Last Observation Carried Forward (LOCF) method will be applied for dealing missing data of the efficacy endpoints.

All comparisons will be conducted with significance level of 0.05, using 2-tailed tests where 95% confidence interval for difference and corresponding *p*-value will be presented.

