Objectives: **Primary Objective:** To assess the safety profile of TWB-103 administered to subjects with diabetic lower limb ulcers

Secondary Objective: To explore the efficacy of TWB-103 administered to subjects with diabetic lower limb ulcers

Endpoints: **Primary Endpoint:** Incidence of adverse events (AEs) and serious adverse events (SAEs). Pre-existing abnormalities are considered as AE or SAE only when the conditions escalate. The following events should be discussed

specifically:

1. Study wound and its periphery: Infection, pain, pruritus/irritation, skin dysfunction/blister, osteomyelitis, cellulitis, edema/swelling and unexpected surgery
2. Non-study area and systemic: Infection, pain, pruritus/irritation, skin dysfunction/blister, osteomyelitis, cellulitis, edema/swelling, unexpected surgery, accidental injury, abnormal lab test and general disorders

Secondary Endpoints:

1. The percentage of subjects with confirmed study wound closure at each week up to 12 weeks.
* Wound closure is defined as “full epithelialization of the wound with the absence of drainage or dressing requirement and without sign of abscess under the epithelium”. An ulcer is considered healed only after wound closure is re-confirmed at the visit 2 weeks later. Therefore, a wound closure should be observed at three consecutive visits (i.e. a duration of 2 weeks) for an ulcer to be deemed as healed.
2. Time (days) to confirmed wound closure for those subjects whose wounds are healed during treatment period and during the study period.
3. Reduction of individual wound area for up to 12 weeks.
4. Reduction of wound area at each week up to 12 weeks.
5. General granulation rate and quality of granulation tissue.
6. Reduction of wound volume for individual subject measured by 3D camera and analysis software up to 12 weeks (only for those subjects who have received the 3D measurement).

Study Population:

Ten subjects aged at least 20 years old (inclusive) with diabetic lower limb ulcers presented for at least 4 weeks are planned to enroll in Taiwan.

Inclusion Criteria

In order to be eligible to participate in this study, an individual must meet all of the following criteria:

1. Adults at least 20 years of age.

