7.2 SUBJECT WITHDRAWAL FROM THE STUDY

A subject may withdraw voluntarily or involuntarily from the trial due to any of the following conditions:

1. The subject voluntarily decides to withdraw her/his consent.
2. The subject's pregnancy is confirmed after enrollment till last dose of TWB-103.
3. The subject received or plans to receive any prohibited therapy as defined in section 6.6.
4. The subject dies or is lost to follow-up.
5. Any pathological event, clinical adverse event, laboratory abnormality, intercurrent illness, or any occurrence or change in the subject's status giving indication to the investigator that further participation in the study may not be the best interest of the subject.
6. The subject develops $>$ Grade 2 skin infection in the ulcer wound, or the treatment for the ulcer wound infection requires subject's hospitalization, intravenous infusion or muscular injection of antibiotics.
7. The subject experiences \geq Grade 1 allergic reaction at least possibly related to the investigational product (section 8.4.3.2).
8. The subject requires a major surgery debridement.

9. The study is terminated prematurely by the investigator, research institution, sponsor, IRB/IEC or regulatory authorities.

If the withdrawal is decided during TWB-103 treatment period, the withdrawn subject will be encouraged to complete the assessments of Week 12, within 1 week of the withdrawal decision, as End of Study (EOS) visit before exiting from the study. Laboratory, pregnancy and PRA tests done within 1 week prior to EOS visit are acceptable.

If the withdrawal is decided in the follow-up period, the withdrawn subject will be encouraged to complete the assessments of Week 36, within 2 weeks of the withdrawal decision, as EOS visit before exiting from the study.

The reason for withdrawal must be recorded. If a subject is withdrawn due to an AE, every effort will be made to follow the event until event resolves or stabilizes at a level acceptable to the investigator.

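### Healing time is estimated by Kaplan-Meier with no censoring or competing-event rule, although several withdrawal reasons reflect a failing wound, so an ordinary run can overstate healing

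*Combined protocol and SAP*

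**What the plan says.** **Analysis.** Section 9.4.1: "Healing time from baseline to wound closure will be estimated by using Kaplan-Meier method". No analysis set, event date, censoring rule or competing-event rule goes with it. The same section adds "The Last Observation Carried Forward (LOCF) method will be applied for dealing missing data of the efficacy endpoints" without saying whether this covers closure status or event times. Further detail is left to a separate SAP, due before data lock.

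**Endpoints (1.1 and 3).** Secondary endpoint 1 is "The percentage of subjects with confirmed study wound closure at each week up to 12 weeks". Secondary endpoint 2 is "Time (days) to confirmed wound closure for those subjects whose wounds are healed during treatment period and during the study period", which is worded for healed subjects only. Section 9.3 analyses efficacy on the ITT and PP sets.

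**Exits.** Section 7.2 lists, among its withdrawal reasons:
- item 3: "The subject received or plans to receive any prohibited therapy as defined in section 6.6"
- item 4: death or loss to follow-up
- item 6: anything above "Grade 2 skin infection in the ulcer wound, or the treatment for the ulcer wound infection requires" admission or injected antibiotics
- item 8: "The subject requires a major surgery debridement"

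A subject withdrawn during treatment is encouraged to attend one end-of-study visit within a week and then leaves. Section 4.4 treats that visit as completion.

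**Contradiction.** For major surgery, 6.7 and 7.2 speak of withdrawal from the study, while 1.1, 4.1 and 7.1 say only that TWB-103 stops. Wound infection is likewise a withdrawal reason in 7.2, but only a reason to stop TWB-103 in 1.1, 4.1, 6.7 and 7.1.

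**The concern.** Kaplan-Meier is valid when a censored subject has the same future chance of the event as those still followed. A subject who leaves because the ulcer is badly infected or needs major debridement plainly does not. Death rules out healing altogether. If such subjects are censored at exit, their share of the probability passes to the remaining, better wounds.

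Two things are at stake. The healing probability and median read from the curve can be too favourable. The 12-week value can also disagree with secondary endpoint 1 in the same report, where an unhealed ITT subject would naturally stay in the denominator. With 10 subjects, one or two exits are enough to show. The study is open-label and the SAP need only be final before data lock, so the rule could be settled after outcomes are known.

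**Working it through.** **Step 1: the plan's own figures.** The documents give no healing rate, withdrawal rate or Kaplan-Meier result to reproduce. The one relevant number is in 9.2: "It is planned to enroll 10 subjects to achieve 8 evaluable subjects". It fits 8 / 0.80 = 10, but no dropout rate is stated, and evaluable there means per-protocol.

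**Step 2: inputs.** n = 10 (9.2), all taken to be in the ITT set. Healing rates for scenarios come from the two trials described in 2.2: 18.3% and 30.0% (control and active), and 38% and 56% (control and active). The number and timing of exits are assumptions, as is the premise that a withdrawn wound does not later heal.

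**Step 3: formulas.** Let d be the healings and r the number at risk at each healing time.
- Exits censored: 1-KM = 1 - product of (1 - d/r), with exits removed from r.
- Exits as competing events (Aalen-Johansen): the sum of (proportion still event-free just before) × d/r.
- Crude closure percentage: healed / n.

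**Step 4: two early exits, then three healings.** After the exits 8 remain at risk.
- 1-KM = 1 - (7/8)(6/7)(5/6) = 1 - 5/8 = 37.5%.
- Aalen-Johansen = (8/10)(1/8) + (7/10)(1/7) + (6/10)(1/6) = 30.0%, equal to the crude 3/10.

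When all exits precede all healings, 1-KM is simply healed / (10 - w), where w is the number of exits:

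| Healed | w = 1 | w = 2 | w = 3 | Crude |
|---|---|---|---|---|
| 3 | 3/9 = 33.3% | 3/8 = 37.5% | 3/7 = 42.9% | 30% |
| 4 | 4/9 = 44.4% | 4/8 = 50.0% | 4/7 = 57.1% | 40% |

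With 4 healed at Weeks 5, 7, 9 and 11 and exits at Weeks 3 and 4, the censored curve reports a median of Week 11. With the exits kept as not healed, the median is not reached.

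**Step 5: timing matters.** With healings at Weeks 6, 9 and 12 and exits at Weeks 3 and 10, 1-KM = 1 - (8/9)(7/8)(5/6) = 35.2%. With both exits after the last healing, or none at all, it is 30.0% and there is no excess.

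**Step 6: average over timings.** Simulation: n = 10, 5,000 trials per cell, healing uniform over Weeks 3 to 12, withdrawal uniform over Weeks 1 to 12. Mean excess of 1-KM over the crude percentage, in points:

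| Healing | 10% withdrawn | 20% | 30% |
|---|---|---|---|
| 18.3% | 1.1 | 2.5 | 4.1 |
| 30% | 2.0 | 4.3 | 6.9 |
| 38% | 2.5 | 5.7 | 9.2 |
| 56% | 4.1 | 8.9 | 15.8 |

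At 20% withdrawal the two summaries differ in 63% to 82% of simulated trials.

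**Step 7: the other readings the text allows.**
- LOCF carries a not-closed status to the end of the window: excess zero.
- Subjects stop TWB-103 but stay in follow-up: they are not censored at that point, so excess zero.
- Endpoint 2 taken literally, healed subjects only: nobody is censored and the curve ends at 100% (4 of 4 in the Step 4 example) whatever the true healing rate.

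**The case against.** The strongest reply is that the censoring is nowhere in the documents. Section 9.4.1 has one Kaplan-Meier sentence, an LOCF rule for efficacy endpoints and a promise of a fuller SAP. If LOCF keeps withdrawn subjects as not closed, the bias vanishes. Nor do the documents state the denominator for the closure percentage, so the mismatch depends on a not-healed rule being applied to one endpoint and not the other. Several sections have these subjects only stopping treatment. The endpoint is secondary, in a single-arm pilot with no hypothesis and a safety primary.

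Much of this stands. A reader might infer that the plan prescribes censoring and that the report must therefore carry two conflicting healing figures. The documents support neither; both follow only from the ordinary default. What does not stand is that the other readings clear the plan. LOCF is not said to govern event times. The healed-only wording overstates healing by another route. The stop-treatment wording contradicts 6.7 and 7.2. If the not-healed reading is intended, it still has to be written down.

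A reader might also take the 2 of 10 non-evaluable subjects as the plan's own wound-failure rate and 7.5 points (37.5% against 30%) as the expected bias. That is not supported. Under 9.3 a subject can miss the per-protocol set through an eligibility failure or too few applications and still be fully followed. The 7.5 points also puts every exit before every healing; the simulated mean at 30% healing and 20% withdrawal is 4.3.

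**Conclusion.** The point holds as a missing rule with a predictable direction. Kaplan-Meier without a censoring or competing-event rule, beside withdrawal reasons tied to wound failure and almost no observation after exit, leaves the healing curve open to informative censoring. Under the ordinary default, 1-KM is at or above the ITT closure percentage and strictly above it whenever a wound-failure exit precedes a later healing.

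At 30% healing the size is about 2 to 7 points on average for 10% to 30% withdrawal. This rests on the assumed rates and timings and on withdrawn wounds not healing later.

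It would go too far to treat every exit as wound failure. Section 7.2 also lists allergic reactions from Grade 1, and the 6.6 list reaches beyond the wound, for example to any other investigational product. Counting those as not healed is an estimand choice and could bias healing downward. The primary safety conclusion is unaffected, but the curve serves the trial's secondary objective and the correction is cheap, so the change should be made.

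**What to change.** In 9.4.1 and the SAP, before outcomes are reviewed:

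1. Estimate time to confirmed closure in all ITT subjects by cumulative incidence (Aalen-Johansen). Competing events are death and withdrawal for study-wound infection, major surgical debridement or prohibited therapy to the study wound. Alternatively, keep these subjects at risk as not healed to the end of the window (Week 12 for the treatment-period curve, end of follow-up for the study-period curve). The two agree exactly only when there is no other censoring.
2. Censor only exits unrelated to the wound. Show allergy exits and other 6.6 therapies as a sensitivity analysis, counted each way.
3. State the event date, the denominator of the closure percentage, whether LOCF applies to closure status, and how closure seen after TWB-103 stops is counted.
4. Reword endpoint 2 in 1.1 and 3 so that it no longer covers healed subjects only. Time among healed subjects can stay as a labelled description.
5. Reconcile the passages that withdraw the subject from the study (6.7, 7.2) with those that only stop TWB-103 (1.1, 4.1, 7.1, and 6.7 for infection), since they determine who remains under observation.

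The cost is protocol and SAP wording and one derived variable for exit type. The healing figure may come out slightly less favourable.
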